4.5.4.2.5 End of study

The following procedures will be performed **at the end of study visit** (in case of completed study) **or 7 days after last drug intake** (in case of the patient drops-out of the study) (**within** ± 3 days) as reported below:

- Adverse event recording;
- Concomitant medications (drugs);
- Significant non-drug therapies (e.g. phlebotomies, transfusions) recording (*if applicable*);
- Physical examination, vital signs (blood pressure, pulse rate, respiratory rate), weight, body temperature and ECOG performance status;
- Blood chemistry: ALT/SGPT, AST/SGOT, ALP, total bilirubin, LDH, creatinine, BUN or Urea (as per site-specific clinical practice; see [Appendix F](#) to convert Urea to BUN), glucose, Na, K, Ca, Cl, Mg, albumin, eGFR determination (according with the Mayo Clinic Quadratic Equation);
- ECG, QTc determination (according with Bazett’s correction formula);
- Haematology: RBC count, HCT, Hb, MCV, MCH, MCHC, WBC count (full and differential), PLT count;
- Spleen evaluation by MRI or CT scan;

- Collection of a blood sample for the quantitative RT-PCR evaluation of JAK2^{V617F} mutational status on peripheral blood (PB) granulocyte;
- Assessment of disease-related symptoms using the MPN-SAF QOL Questionnaire [24, 32];
- Bone marrow histological evaluation, in patients who have consented to this optional exploratory research, and that have not any medical contraindication to bone marrow sampling as judged by the Investigator;
- Therapeutic response evaluation according to the clinico-haematological ELN response criteria [21] (see [paragraph 4.6.1](#));
- Therapeutic response evaluation according to the “new” ELN criteria (i.e. **revised** ELN response criteria) [33] (see [paragraph 4.8.7](#));
- Used/unused/partially used Givinostat supply return and Givinostat accountability.

In case the patient drops-out the study during the first 3 Cycles (i.e. before the Day 28 of Cycle 3), the bone marrow histological evaluation has not to be performed at End of Study visit.

In case the patient completes the study (i.e. performs all the evaluations requested to be done at the Day 28 of Cycle 6), the evaluation performed at the Cycle 6 Day 28 visit can be counted for the End of Study visit.

In addition, in case the patient completes the study (i.e. performs all the evaluations requested to be done at the Day 28 of Cycle 6) and she/he is eligible to continue the study drug treatment in the long-term study (i.e. Study DSC/11/2357/44), the evaluation performed at the Cycle 6 Day 28 visit of this study can be also counted for the pre-treatment evaluations of the Study DSC/11/2357/44, provided that no difference in the evaluation is present between the two studies (e.g. haematological and biochemical evaluations). **No additional Givinostat study (i.e. Study DSC/12/2357/45)-specific assumption has to be done at the completion of the Day 28 of Cycle 6.** Indeed, in case the patient completes the study (i.e. performs all the evaluations requested to be done at the Day 28 of Cycle 6 of this study), she/he is eligible to continue the study drug treatment in the long-term study (i.e. Study DSC/11/2357/44) and she/he receive the written authorization of the treatment from the Sponsor of their designee (i.e. a patient’s confirmation form that includes the patient ID to use into the Study DSC/11/2357/44), the patient will continue the study drug treatment into the Study DSC/11/2357/44, receiving the study (i.e. Study DSC/11/2357/44)-specific drug to be taken.

As reported also in the [paragraph 4.3.3](#), if the patient discontinues for any reason (including discontinuation for pregnancy), with drug related adverse event ongoing at study end, he/she must be followed until resolution or stabilization of the event or until it is reasonable to consider the event not drug related any more or until the start of a new treatment, whichever occurs first.

If the patient needs to take one of the concomitant medications included in list of “Drugs with risk of Torsades de Pointes” (see [Appendix C](#)) the treatment with Givinostat is to be promptly discontinued and the patient must leave the study.

In case of multiple reasons (e.g. patient withdraws the consent for toxicity), “adverse events” should be indicated as the primary reason whenever applicable. All relevant information related to the reason for treatment discontinuation including contributory factors must be included on the CRF.

A complete end of study visit must be performed by 7 days after the last drug intake for any patient permanently discontinuing study treatment. Should any drug-related AE still be ongoing beyond the last scheduled visit, this must be followed at subsequent follow-up visits until recovery. If a patient does not return for a scheduled visit, every effort should be made to contact the patient. In any circumstance every effort should be made to complete and report the observations as thoroughly as possible. All relevant information related to the reason for treatment discontinuation including contributory factors must be included on the CRF.

At study close-out, and as appropriate during the course of the study, the Investigator will return all used and unused study drug, packaging, drug labels, and the completed drug forms to Italfarmaco S.p.A., Dipartimento di Tecnica Farmaceutica, [name] or their designee.

Only in some particular cases, after the authorization of Italfarmaco S.p.A. (or after a signed agreement between the investigational site and Italfarmaco S.p.A.), these materials can be destroyed locally.

4.5.4.3 Information to be collected on screening failures

Patients who sign an informed consent form but who do not start study treatment for any reason will be considered a screen failure. The reason for screen failure and each patient’s demographic information will be entered in the CRF within 2 days.

4.6 Efficacy assessments

[Appendix A](#) and [paragraph 4.5.4](#) summarize timing information.

4.6.1 Criteria for assessing clinico-haematological improvement

Disease response will be evaluated according to the following clinico-haematological ELN criteria [21] (see [paragraph 4.6.1](#)) after 3 and 6 cycles (i.e. at weeks 12 and 24, respectively) of treatment with Givinostat both in **Part A** (exploratory endpoints) and in **Part B** (primary and secondary endpoints, respectively).

- **Complete response:**
 1. HCT < 45% without phlebotomy, **and**
 2. Platelets $\leq 400 \times 10^9/L$, **and**
 3. WBC $\leq 10 \times 10^9/L$, **and**
 4. Normal spleen size, **and**
 5. No disease-related systemic symptoms (i.e. pruritus, headache, microvascular disturbances).

- **Partial response:**

Patients who do not fulfil the criteria for complete response and

 1. HCT < 45% without phlebotomy, **or**
 2. Response in 3 or more of the other criteria.

- **No response:** any response that does not satisfy partial response.

Only in case the enrolment in **Part A** is slow (i.e. < 5 patients enrolled in 3 months) and the eligibility for this part of the study may be expanded to all patients with cMPN, disease response for this part of the study will be evaluated according to the clinico-haematological ELN and EUMNET criteria [29] after 3 and 6 cycles of treatment with Givinostat, in ET and MF patients, respectively.

For ET (from the clinico-hematological ELN response criteria):

- **Complete response:**
 1. Platelets $\leq 400 \times 10^9/L$, **and**
 2. No disease related systemic symptoms (i.e. pruritus, headache, microvascular disturbances), **and**
 3. Normal spleen size, **and**
 4. WBC $\leq 10 \times 10^9/L$.

- **Partial response:**

Patients who do not fulfil the criteria for complete response and

 1. Platelet count < $600 \times 10^9/L$, **or**
 2. Platelet count decrease > 50% from baseline.

- **No response:** any response that does not satisfy partial response.

Both for PV and ET patients, all phlebotomies performed in the first 3 weeks of treatment will **not** be counted to assess the clinico-haematological response.

For MF (from EUMNET response criteria)

- **Complete response:** complete response in anemia, splenomegaly, constitutional symptoms, platelet and leukocyte count.
 1. Complete response in anaemia: Haemoglobin ≥ 12 g/dL for transfusion-independent patients or ≥ 11 g/dL for transfusion-dependent patients (applicable only for patients with baseline haemoglobin level of < 10 g/dL);
 2. Complete response in splenomegaly: Spleen not palpable;
 3. Complete response in constitutional symptoms: Absence of constitutional symptoms (fever, drenching night sweats, or $\geq 10\%$ weight loss);
 4. Complete response in platelet count: Platelet count $150-400 \times 10^9/L$;
 5. Complete response in leukocyte count: Leukocyte count $4-10 \times 10^9/L$.

- **Major response:** Any response in both anaemia and splenomegaly without progression in constitutional symptoms **or** complete response in anaemia without progression in splenomegaly **or** partial response in anaemia in a baseline transfusion-dependent patient combined with response in constitutional symptoms without progression in splenomegaly **or** any response in splenomegaly combined with response in constitutional symptoms without progression in anaemia.
 1. Partial response in splenomegaly: Either $\geq 50\%$ decrease in spleen size if baseline ≤ 10 cm from left costal margin (LCM) or $\geq 30\%$ decrease if baseline > 10 cm from LCM.
 2. Partial response in platelet count: A $\geq 50\%$ decrease in platelet count if baseline $> 800 \times 10^9/L$ or platelet count increase by $\geq 50\% \times 10^9/L$ if baseline $< 100 \times 10^9/L$.
 3. Partial response in leukocyte count: A $\geq 50\%$ decrease in leukocyte count of baseline $> 20 \times 10^9/L$ or leukocyte count increase by $\geq 1 \times 10^9/L$ if baseline $< 4 \times 10^9/L$
 4. Progression in anaemia: A hemoglobin decrease of ≥ 2 g/dL **or** a 50% increase in transfusion requirement **or** becoming transfusion dependent
 5. Progression in splenomegaly: A $\geq 50\%$ increase in spleen size if baseline ≤ 10 cm from LCM **or** a $\geq 30\%$ increase if baseline > 10 cm from LCM.
 6. Progression in constitutional symptoms: Appearance of constitutional symptoms.

- **Moderate response:** Complete response in anaemia with progression in splenomegaly **or** partial response in anaemia without progression in splenomegaly **or** any response in splenomegaly without progression in anaemia and constitutional symptoms.

- **Minor response:** Any leukocyte- **or** platelet-based response without progression in anaemia, splenomegaly, **or** constitutional symptoms.
- **No response:** Any response that does not qualify at least as minor response.

In all cases (PV, ET and MF patients), the disease-related systemic symptoms will be evaluated directly by patients according to MPN-SAF QOL questionnaire [24, 32].

In all cases, the response status of the patient may be reviewed by a panel of independent Investigators, *if necessary*.

4.6.2 Criteria for determination of MTD

Once all patients enrolled in **Part A** have been treated for at least 1 cycle, the study team (see [paragraph 4.1.1.2](#)) will determine the MTD to be used in **Part B** based on the safety and tolerability profile of Givinostat observed as well as the PK and PD data, *if applicable*.

4.6.3 Criteria for characterization of PK

Plasma concentrations from **Parts A** and **B** will be evaluated by dose and time point for all patients and time points with at least one PK assessment.

4.6.4 The Efficacy Population

The analysis sets are defined in the [paragraph 6.2.1](#).

Patients with a disease-related global deterioration of health status requiring discontinuation of treatment without objective evidence of disease progression at that time should be reported in CRF as disease progression clinically assessed. Every effort should be made to document the objective progression even after discontinuation of treatment.

The response status of the patient may be reviewed by a panel of independent investigators, *if necessary*.

4.7 Safety assessments

Safety and tolerability will be evaluated by monitoring haematology and blood chemistry, urinalysis (only in the first cycle of **Part A**), by measurement of physical

examination, vital signs, weight, body temperature, ECOG performance status, ECG assessment and evaluation, QTc determination and adverse events recording at scheduled times as described above. [Appendix A](#) and [paragraph 4.5.4](#) summarize timing information.

All significant findings already present during the screening visit before drug administration will be reported in the appropriate section of CRF (Medical History section or Current Medical Conditions section). Significant findings occurring after patient enrolment, identified as Adverse Event (AE), will be recorded in Adverse Event section of CRF.

The following criteria will use to assess the safety and tolerability both in **Part A** (primary endpoint) and after 3 and 6 cycles (primary and secondary endpoints, respectively) in **Part B**:

- Number of patients experiencing adverse events.
- Type, incidence, and severity of treatment-related adverse events, graded according to Common Terminology Criteria for Adverse Events (CTCAE v. 4.03, 14th June 2010).

4.7.1 Laboratory evaluations

The following laboratory examinations (haematology, blood chemistry and urinalysis) will be performed at each investigational unit by a local laboratory co-operating with the Investigator following its own procedures:

- **Haematology:** RBC count, HCT, Hb, MCV, MCH, MCHC, WBC count (full and differential), PLT count;
- **Blood chemistry:** ALT/SGPT, AST/SGOT, ALP, total bilirubin, LDH, creatinine, BUN or Urea (as per site-specific clinical practice; see [Appendix F](#) to convert Urea to BUN) , glucose, Na, K, Ca, Cl, Mg, albumin, eGFR determination (according with the Mayo Clinic Quadratic Equation);
- **Urinalysis:** pH, specific gravity, protein, glucose.

The required amount of blood and urine will be collected at each visit as scheduled above. [Appendix A](#) and [paragraph 4.5.4](#) summarize timing information.

All results of laboratory examinations will be entered into the appropriate CRF sections. The original laboratory print-outs will be filed in the patient file at the study site.

Of note, if the ECG evaluation demonstrates a prolonged QTc interval (i.e. a QTc interval ≥ 450 msec), two additional ECG evaluations over a brief period of time (i.e. 5 minutes between each recording) must be performed. The averaged value of these three ECG evaluations has to be used for the evaluation of the QTc interval of the related visit. In the CRF all the performed ECG evaluations have to be entered as well as the average value of multiple ECG evaluation, *if necessary*.

4.7.2 Clinical safety assessments

Clinical safety assessments will include a thorough physical examination, vital signs assessment (respiratory rate, pulse rate and sitting blood pressure will be measured after 5 minutes of rest), weight, body temperature, ECOG performance status, ECG assessment and evaluation, QTc determination (according with Bazett's correction formula, [Appendix D](#)).

[Appendix A](#) and [paragraph 4.5.4](#) summarize timing information.

All results of the above mentioned clinical safety assessments will be entered into the appropriate CRF sections. The original print-outs related to these evaluations, including the ECG and QTc recording, will be filed in the patient file at the study site.

Of note, if the ECG evaluation demonstrates a prolonged QTc interval (i.e. a QTc interval ≥ 450 msec), two additional ECG evaluations over a brief period of time (i.e. 5 minutes between each recording) must be performed. The averaged value of these three ECG evaluations has to be used for the evaluation of the QTc interval of the related visit. In the CRF all the performed ECG evaluations have to be entered as well as the average value of multiple ECG evaluation, *if necessary*.

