4.3.2 Exclusion criteria

Patients must **NOT** meet any of the following criteria to be eligible for study entry:

1. Active bacterial or mycotic infection requiring antimicrobial treatment;
2. Pregnancy or nursing;
3. A clinically significant QTc prolongation at baseline (e.g. repeated demonstration of a QTc interval ≥ 450 msec);
4. Use of concomitant medications known to prolong the QT/QTc interval;
5. Clinically significant cardiovascular disease including:
 - a) Uncontrolled hypertension despite medical treatment, myocardial infarction, unstable angina within 6 months from study start;
 - b) New York Heart Association (NYHA) Grade II or greater congestive heart failure;
 - c) History of any cardiac arrhythmia requiring medication (irrespective of its severity);
 - d) A history of additional risk factors for TdP (e.g. heart failure, hypokalemia, family history of Long QT Syndrome);
6. Known positivity for HIV;
7. Known active HBV and/or HCV infection;
8. Platelet count $< 100 \times 10^9/L$ within 14 days before enrolment (i.e. the receipt of the Patient ID);
9. Absolute neutrophil count $< 1.2 \times 10^9/L$ within 14 days before enrolment (i.e. the receipt of the Patient ID);
10. Serum creatinine $> 2 \times$ ULN;
11. Total serum bilirubin $> 1.5 \times$ ULN except in case of Gilbert's disease;
12. Serum aspartate aminotransferase/alanine aminotransferase (AST/ALT) $> 3 \times$ ULN;
13. History of other diseases (including active tumours), metabolic dysfunctions, physical examination findings, or clinical laboratory findings giving reasonable suspicion of a disease or condition that contraindicates use of an investigational drug or that might affect interpretation of the results of the study or render the subject at high risk from treatment complications;
14. Prior treatment with a JAK2 or HDAC inhibitor or participation in an interventional clinical trial for cMPN, including PV, ET or MF;
15. Systemic treatment for cMPN other than aspirin/cardio aspirin;
16. Hydroxyurea within 28 days before enrolment (i.e. the receipt of the Patient ID);
17. Interferon alpha within 14 days before enrolment (i.e. the receipt of the Patient ID);
18. Anagrelide within 7 days before enrolment (i.e. the receipt of the Patient ID);
19. Any other investigational drug or device within 28 days before enrolment (i.e. the receipt of the Patient ID);
20. Patient with known hypersensitivity to the components of study therapy.

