6.2.8 Other Safety evaluation

All patients who receive at least one dose will be included in the safety evaluation. Safety data including laboratory evaluations, physical exams, ECG monitoring and vital signs assessments will be summarized at each time point. Descriptive statistics

(arithmetic mean, standard deviation, median, minimum and maximum) will be calculated for quantitative safety data as well as for the difference from baseline, if applicable. Frequency counts will be compiled for classification of qualitative safety data. In addition, a shift table describing out of normal range shifts (low/normal/high values) will be provided for clinical laboratory results. A normal-abnormal shift table will also be presented for physical exam and ECG results.

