10.4 Appendix D: Bazett's correction formula

BAZETT'S CORRECTION FORMULA

$$QTc = QT / RR^{0.5}$$

RR = interval from the onset of one QRS complex to the onset of the next QRS complex, measured in seconds.

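### Bazett is the only QT correction in a single-arm study, so the descriptive QTc change may partly reflect heart rate; report Fridericia beside it

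*Protocol*

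**What the plan says.** The formula is stated consistently, in section 4.7.2 as "ECG assessment and evaluation, QTc determination (according with Bazett's correction formula". Sections 4.5.1 and 4.7.2, the visit schedules in 4.5.4 and the flow-charts in Appendix A all use Bazett. Appendix D gives QTc = QT / RR^0.5 with "RR = interval from the onset of one QRS complex to the onset of the next QRS complex, measured in seconds".

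QTc has three uses:

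- Entry: exclusion criterion 3 in section 4.3.2 refers to "A clinically significant QTc prolongation at baseline (e.g. repeated demonstration of a QTc interval" at or above 450 msec).
- Repeat ECGs: a first reading at or above 450 msec triggers two more, and "The averaged value of these three ECG evaluations has to be used for the evaluation of the QTc interval of the related visit" (section 4.7.2).
- Reporting: under section 6.2.8, "Safety data including laboratory evaluations, physical exams, ECG monitoring and vital signs assessments will be summarized at each time point". Differences from baseline are given for quantitative safety data where applicable, and "A normal-abnormal shift table will also be presented for physical exam and ECG results".

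Pulse rate is also recorded: "respiratory rate, pulse rate and sitting blood pressure will be measured after 5 minutes of rest" (section 4.7.2). The safety endpoint in section 4.7 is built on adverse events ("Number of patients experiencing adverse events"), not on QTc.

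**The concern.** The protocol treats QT prolongation as a declared risk. It excludes patients with prolonged QTc, QT-prolonging medication or risk factors for torsades de pointes (section 4.3.2, criteria 3, 4 and 5d). It bans drugs known to provoke torsades (section 4.4.5) and adds the repeat-ECG rule. The descriptive QTc summaries will therefore be read closely.

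Those summaries rest on one correction formula and have no comparator. If mean heart rate rises on treatment and Bazett over-corrects, a QTc increase appears that has nothing to do with repolarisation. If heart rate falls, a real prolongation can be partly hidden. Averaging three ECGs reduces random error but leaves a rate-dependent bias in place.

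Part B offers a concrete route. The only scheduled pre-treatment ECG is at screening. After eligibility is confirmed, patients with HCT of 45% or more must be phlebotomised (section 4.5.4.2.1). The Day 1 list contains no ECG (section 4.5.4.2.2), and the next scheduled one is at Cycle 1 Day 28 (section 4.5.4.2.3). Baseline and on-treatment ECGs can thus lie on either side of a phlebotomy. Part A is less exposed, because an ECG is repeated before the first dose on Day 1 (section 4.5.4.1.2).

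**Working it through.** The protocol states no figure on this point that could be reproduced. The check takes the Appendix D formula and asks how it behaves when heart rate changes and repolarisation does not.

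**Inputs.** From the protocol: QTcB = QT / RR^0.5 with RR in seconds (Appendix D), and the 450 msec threshold (section 4.3.2). Assumed, because the documents are silent: QT of 415 msec at RR = 1 s; true QT-RR exponent k of 1/3, 0.42 or 0.5; heart rate (HR) of 70 bpm at baseline.

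**Formulas.** If QT = 415 × RR^k and RR = 60/HR, then

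- QTcB = 415 × (HR/60)^(0.5 − k)
- QTcF = QT / RR^(1/3) = 415 × (HR/60)^(1/3 − k)

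QTcB is free of heart rate only at k = 0.5, and QTcF only at k = 1/3.

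**Worked case, k = 1/3.** At 70 bpm QTcB = 415 × (70/60)^(1/6) = 425.8 msec. At 80 bpm it is 415 × (80/60)^(1/6) = 435.4 msec. The change is +9.6 msec with no change in repolarisation.

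**Spurious change (msec) by exponent and heart-rate change:**

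| Exponent k | QTcB, 70 to 80 bpm | QTcB, 70 to 90 bpm | QTcB, 70 to 60 bpm | QTcF, 70 to 80 bpm |
|---|---|---|---|---|
| 1/3 | +9.6 | +18.2 | −10.8 | 0 |
| 0.42 | +4.5 | +8.5 | −5.1 | −4.7 |
| 0.5 | 0 | 0 | 0 | −8.9 |

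**Share of ECGs at or above 450 msec by Bazett.** Simulated with a true rate-independent QTc of mean 415 and SD 15 msec, and heart-rate SD 10 bpm (all assumed):

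| Exponent k | Mean 65 bpm | Mean 75 bpm | Mean 85 bpm |
|---|---|---|---|
| 1/3 | 5% | 14% | 28% |
| 0.42 | 2% | 4% | 7% |
| 0.5 | 1% | 1% | 1% |

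The artefact therefore runs from nothing to a size that could be mistaken for a drug effect, depending on an exponent that the documents do not give. The last column of the first table limits the remedy: QTcF has its own error, of opposite sign, whenever k exceeds 1/3.

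**The case against.** Four objections carry weight.

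1. *This belongs in the SAP.* Section 6.2 calls itself an outline and leaves full detail to a plan that is not shown. That plan may add a second correction, and nothing forbids it. However, the protocol does not leave the correction open: it fixes one formula at every ECG visit. Whether QT and RR are captured is also a CRF question, and section 6.2 promises the SAP only before database lock.

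2. *The heart-rate premise is inferred.* This stands. No section says that phlebotomy, falling haemoglobin or givinostat changes heart rate. Table 3 gives rules for anaemia if it occurs; it does not predict it.

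3. *QTc carries little formal weight.* This also stands. QTc is not an endpoint, no test is planned, and neither Table 3 nor section 4.3.3.3 has a QTc-specific dose or stopping rule. Pulse rate is summarised with the vital signs, so a large mean shift would be visible, although the planned summaries do not link it to QTc.

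4. *Fridericia is no better in the middle of the range.* At exponent 0.42 the two corrections err by almost the same amount in opposite directions.

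Three stronger readings are tempting, and the documents do not support them. A reader might infer that any heart-rate change must appear as a QTc change; that fails at exponent 0.5. A reader might infer that the QTc result is confounded; without a documented heart-rate shift or QT-RR relation, the most that can be said is that it may be. A reader might infer that Fridericia should replace Bazett as the basis for the conclusion; the table above rules that out.

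**Conclusion.** The point holds as a conditional and modest one. Bazett is the sole correction in a single-arm study where QT is a declared risk. If heart rate differs between the baseline and on-treatment ECGs, and the true exponent is not 0.5, the descriptive QTc change and the 450 msec share may partly reflect heart rate, and the design cannot separate that from a drug effect. For a 10 bpm rise from 70 bpm at 415 msec the size is 0 to +9.6 msec over exponents from 0.5 to 1/3. That range rests on assumed values for the exponent, the QT level and the heart-rate change. The point concerns descriptive safety reporting only and does not touch the primary efficacy result.

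**What to change.** Add to section 6.2.8 that QT and RR (or ECG heart rate) are captured from the tracings already taken. Report QTcF = QT / RR^(1/3), which equals QTcB × RR^(1/6), beside QTcB: value, change from baseline and outliers, with the ECG heart-rate change at the same visit. Where three ECGs are averaged, compute QTcF on each tracing and then average. Read a QTc effect as robust only if both corrections agree, and do not make QTcF the sole basis.

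The ECG's own heart rate should be used rather than the vital-signs pulse. On Part A Day 1 after dosing, the ECG is at 3 hours and the vital signs at 4 hours (section 4.5.4.1.2).

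Leave the 450 msec entry and repeat-ECG rules unchanged.

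Cost: two extra data fields if QT and RR are not already in the CRF (the protocol does not say that they are entered separately), plus extra table columns. No new visits, procedures or patients are needed.
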